7.8 Subject Follow-up after trial completion or early termination

After completion of the last study visit, the subject will continue to participate in the site-specific Heart Failure Follow-up program.

8 STUDY PROCEDURES AND SCHEDULES

8.1 Study Procedures and Evaluations

The following sections describe the procedures to be completed throughout the conduct of the study. Subjects are to be assessed by the same Investigator or site personnel whenever possible. The Schedule of Study Procedures is described here in Section 8 and in Appendix 14.1. Every attempt should be made to perform evaluations at the designated time points. However, for visits conducted at Month 1 and 3 there is a window of +7 days, for visits at Month 6 there is a window of +14 days and after Month 6 (Month 12, 18, 24 and Year 3, 4 and 5) there is a window of +30 days.

8.1.1 Study Eligibility Review

Inclusion and exclusion criteria will be reviewed during the Screening period for all subjects to determine study participation eligibility using the following process:

[figure not shown]

Figure 10: Enrollment Process

8.1.2 Informed Consent Procedure

Before enrolling the subject in the trial, i.e., before any trial-related examination is performed, a written Informed Consent Form (ICF) must be obtained. Each potential participant shall be informed of the aim of the trial and what participation entails. They shall be supplied with an Information Sheet summarizing the details of the trial. Ample time should be given to the subjects to consider their participation. Agreement to participate in the trial is to be confirmed by the subject and the Principal Investigator (or authorized designee) by signing and dating the consent form. Documentation of this procedure is required in the medical record.

Standard-of-care assessments obtained within the 30 days prior to consent for screening may be used: 1) to confirm eligibility; and 2) for screening measurements, if the subject meets eligibility criteria and signs the ICF. Echocardiograms obtained within 3 or 6 months prior to ICF may be used for screening measurements.

Vulnerable populations will not be included in this trial.

8.1.3 Point of Contact

A point of contact of where to obtain additional information on the trial, on the rights of the subject and whom to contact in the event of trial-related injury will be provided to each subject. This information will be specified in the ICF.

8.1.4 Informing the Subject's General Practitioner (EU only)

In certain applicable countries, and in cases where the subject is typically treated by a general practitioner or other equivalent Health Care Provider (HCP), then with the subject's agreement this HCP is to be informed of the subject's participation in the trial at enrollment. The provider should be informed of the title of the trial, date of enrollment into the trial, and the dates of the outstanding visits. The communication with the general practitioner should be documented in the subject's medical record.

8.1.5 Subject Demographics

Subject demographics will be collected and identified by a non-identifying number on the eCRF including sex, gender, year of birth, weight, height, race, and ethnicity. Subject BMI will also be recorded.

8.1.6 Cardiac/Medical and Surgical History

Medical and surgical history, including cardiac history, will be obtained at Screening and updated at the Cordella PA Sensor Implant Visit prior to the implant procedure as follows:

- General medical history
- Primary cardiac diagnosis (ischemic cardiomyopathy/ nonischemic cardiomyopathy)
- Previous cardiac history incl.:
 - Coronary Artery Bypass Grafting (CABG)
 - Percutaneous coronary intervention (PCI)
 - Hypertension
 - Ventricular Tachycardia
 - Atrial Fibrillation
 - ICD / CRT
- Duration of Heart Failure/ NYHA class
- Cardiopulmonary Exercise Testing (CPX) Results (if available)
- Number of hospitalizations in past year for cardiac reasons and HF
- Smoking, Alcohol, Drug Use

With co-morbidities to be identified as:

- Diabetes (diet, oral, insulin)
- COPD
- Chronic Kidney Disease
- Carotid artery disease, Peripheral vascular disease

8.1.7 Physical Examination and Vital Signs

A full physical examination including chest circumference* will be obtained at Screening. An abbreviated physical examination will be obtained at the Cordella PA Sensor Implant Visit prior to the implant procedure and at Month 1, 6, 12, 18, 24 and Year 3, 4 and 5. All physical examinations will be conducted by a licensed physician, NP, registered nurse (RN), or physician assistant (PA) in accordance with local laws and regulations.

Vital signs via Cordella System will be obtained at all study visits. BP, HR, arterial oxygen saturation (SpO₂) level, and weight. Height and BMI will be measured at Screening only.

*If chest circumference is above 55 inch/ 1400 mm please provide CT scan in Screening Package for PROACTIVE-HF Clinical Eligibility review. If a preexisting CT exists, which was taken within the last 12 months, the CT does not have to be repeated at the time of screening.

8.1.8 Electrocardiograms (ECG)

A 12-lead electrocardiogram (ECG) will be obtained at Screening, Month 6, 12, 24 and Year 3, 4 and 5. For all ECGs, the Investigator will write their findings on the ECG as either:

- "Normal ECG"
- "Abnormal ECG, Clinically Significant"
- "Abnormal ECG, Not Clinically Significant"

Subsequent ECGs may be obtained at the discretion of the Investigator. ECGs will be signed and dated by the Investigator. The original ECG tracing will be retained in the subject's records at the study site and a copy will be provided to the Sponsor if requested.

8.1.9 Clinical Laboratory Tests

Blood samples will be obtained for local clinical laboratory tests (hematology and serum chemistry) at Screening, Month 6, 12, 24 and Year 3, 4 and 5. Additionally, urine samples will be obtained for testing, including pregnancy tests for females at Screening. Appropriate accreditation for all laboratories as well as the reference ranges for each of the laboratory parameters measured with a description of the methods to be used in the study must be provided to Endotronix prior to initiation of the study. Changes in the reference ranges or in the methodology during the trial are to be communicated to Endotronix or representative.

Hematology	Biochemistry		Urinalysis (Screening only)
Hemoglobin	NT-pro BNP*	CRP	Glucose
Hematocrit	Sodium	SGOT (AST)	Protein
Leucocytes	Potassium	SGPT (ALT)	Specific gravity
Platelets	Creatinine	Cholesterol	pH
Lymphocytes	Total Bilirubin	Uric Acid	Ketones
aPTT**	Blood Urea Nitrogen (BUN)/ Urea		Bilirubin
INR**	Total Protein		Urobilinogen
	Albumin		Nitrite
* also captured at Month 1, 3 and 18 ** if indicated			Blood
			Leukocytes
			Urine Pregnancy Test (females)

The results of laboratory tests will be returned to the investigator, who is responsible for filing and reviewing these results together with the data in the eCRF. The investigator is responsible for transcribing laboratory results to the eCRF. The investigator will maintain a copy of the laboratory accreditation and the reference ranges for each laboratory used.

The total amount of blood per subject for laboratory tests will be approximately 100 mL.

8.1.10 Echocardiogram

Echocardiograms will be performed at Screening, Month 12 and Year 3, 4 and 5.

Echocardiograms will determine the following parameters:

- LVEF
- Left ventricular mass
- Left ventricular volume
- Left Ventricular End Diastolic Diameter (LVEDD)
- Systolic pulmonary artery pressure (sPAP)
- Mean pulmonary artery pressure (mPAP)
- Diastolic pulmonary artery pressure (dPAP)
- Right atrial pressure (RAP)
- Left atrial size
- Left atrial volume
- Mitral regurgitation
- Tricuspid regurgitation

If an echocardiogram has been performed within 3 months of Screening, that LVEF may be acceptable to determine study eligibility. While an echocardiogram within 3 months of the screening visit date is preferable. In case this is not possible, Endotronix will accept an echocardiogram from within 6 months of Screening provided the patient does not have a standard of care indication for an echocardiogram during this interval.

8.1.11 NYHA Functional Classification

AHA/ACC and NYHA classification guidelines can be found in Appendix 14.2. The NYHA Functional classification categorizes the extent of HF by placing patients in one of four categories based on how much they are limited during physical activity and symptoms of shortness of breath and/or angina. Determination of NYHA classification will be performed by an independent assessor (defined as a physician or qualified PA, RN or NP not directly involved with this clinical trial).

NYHA Functional Classification will be obtained at all study visits and must be NYHA Class III for study entry.

8.1.12 Six (6) Minute Walk

Subjects will complete a six (6) minute walk test at Screening, Month 6, 12 and 24 as well as at Year 3, 4 and 5. In addition, PAP Measurements will be obtained before and after 6-minute walk test after unblinding at Month 12, 24 and Year 3, 4 and 5.

If the Subject is unable or unwilling to perform the 6-minute walk test, the distance recorded should be left blank. Instructions for the procedure are found in Appendix 14.3.

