10.8 Study Retention and Handling of Missing and Incomplete Data

Every effort will be made to collect all data points in the study. Endotronix plans to minimize the amount of missing data by appropriate management of the prospective clinical trial, proper screening of study subjects, and training of participating investigators, monitors and study coordinators. The primary efficacy analysis will be based on the mITT population and the primary safety analyses will be based on the population of patients who underwent a device implant. The primary analysis methods naturally handle missing data by censoring patients who have dropped out. Sensitivity analyses to missing data will be conducted. For the primary safety analyses, the endpoints can be considered as dichotomous and the extreme cases as well as a tipping point analysis can be presented. Reasons for missing data (e.g., patient withdrawal of consent, death, etc.) will be captured and summarized.

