Sample size calculations for the first secondary endpoint were performed in PASS 2021 and based on an assumed population event rate of 0.55, the sample size of 450 subjects would provide approximately 95% power for the secondary endpoint based on a one-sided 0.025 alpha level. If 406 subjects are followed for 12 months, approximately 95% power will be provided, so that the planned sample size is sufficient in light of potential attrition.

Formal hypothesis testing for the purposes of labeling claims for the first secondary efficacy endpoint will only be performed if the null hypothesis for the primary efficacy endpoint is successfully rejected.

This gatekeeping approach preserves the overall type I error rate. Any other calculated p-values and confidence intervals for secondary endpoints will be nominal, without adjustment for multiple comparisons.

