3.3. Secondary Efficacy Endpoints

1. Incidence of HF Hospitalizations or all-cause mortality at 12 months
2. Number of HF Hospitalizations at 6 and 12 months post-implant compared to the number of HF Hospitalizations in the 6 and 12 months prior to implant
3. Comparison of the number of HF Hospitalizations or Emergency Department/ Hospital Outpatient IV diuretic visits of Cohort #1 and Cohort #2 + #3 at 6 and 12 months post implant
4. Change of N-terminal pro B-type Natriuretic Peptide (NT-proBNP) from Baseline through 6 and 12 months
5. Combined outcome of:
 - a. First and recurrent HF Hospitalizations
 - b. Heart failure Emergency Department/ Hospital Outpatient IV diuretic visits
 - c. all-cause mortalityat 6 months, added together with equal weighting into a total number of events.
6. Heart failure hospitalization or HF Emergency Department/ Hospital Outpatient IV diuretic visits at 6 and 12 month
7. Cardiac and all-cause mortality
8. Days Alive and Out of Hospital (DAOH)
9. Intravenous (IV) diuretic visits
10. Heart failure related Medication changes
11. Change in PAP:
 - a. From Baseline through 6 and 12 months in subjects with a baseline mPAP
 - i. above target range
 - ii. within or below target range
 - iii. Overall
 - b. Before and after 6-Minute Walk Test
12. Percentage of device success as documented by ability of the System to successfully transmit PAP data
13. Subject Outcome Measures, measured by Kansas City Cardiomyopathy Questionnaire (KCCQ)
14. Functional status improvement, as measured by NYHA and 6-Minute Walk Test
15. Health Economic Analysis (will be covered separately)

This document is confidential.

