5.3. Missing Data

It is anticipated that there will be little or no missing data that would impact the ability to assess the primary endpoint. The primary efficacy analysis will be based on the mITT population and the primary safety analyses will be based on the population of subjects who underwent a device implant. The primary analysis methods naturally handle missing data by censoring subjects who have dropped out. For the primary safety analyses, the endpoints can be considered as dichotomous and the extreme cases as well as a tipping point analysis can be presented.

For all other analysis, missing data will not be replaced.

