7.1.17. Functional status improvement measured by NYHA and 6-Minute Walk Test

NYHA functional classification: The subject's functional status is assessed by a qualified individual at the institution, who is not directly involved with this clinical trial, by utilizing the NYHA functional classification, described in the Protocol Appendix 14.2.

The NYHA functional classification categorizes the extent of heart failure by placing subjects in one of four (I, II, III, IV) categories based on how much they are limited during physical activity and symptoms of shortness of breath and/or angina.

This document is confidential.

NYHA functional classification will be obtained at all study visits as described in [Appendix 1: Time and Event Schedule](#) and must be NYHA Class III for study entry.

Shifts in NYHA functional classification from baseline over all post-baseline visits will be presented.

Six (6) Minute Walk: Subjects complete a six (6) minute walk test at the study visits described in [Appendix 1: Time and Event Schedule](#). Total distance walked (meters) will be collected and analyzed by means of descriptive statistics including the absolute value and change from baseline by visit.

Analysis will be done based on mITT population, PP population, and Cohort #1 population. Prior to the date of cut-off for the main analysis, it will be confirmed, if analysis based on PP population will be required.

This document is confidential.

8. Safety

The population used for safety analyses will be the ITT. Safety will be assessed on the basis of adverse events (AEs), clinical laboratory data, ECG parameters, Echocardiograms, physical examinations, and vital signs. Primary safety endpoint will be analyzed based on mITT. In addition, AEs will be analyzed based on Cohort #1 population. Primary safety endpoints will also be repeated on ITT, PP population and Cohort #1 population. Secondary safety endpoints will also be analyzed based on PP population and Cohort #1 population. For CEC related endpoints, tables and figures will be repeated using CEC adjudication results

Adverse events and other safety analyses will also be assessed. No formal statistical hypothesis tests will be conducted. Analyses will involve Kaplan-Meier curves for time to event outcomes, descriptive statistics (n, mean, standard deviation, median, minimum, and maximum) for quantitative outcomes, and count and frequency results for categorical outcomes.

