8.1.2. Sensitivity analysis

Two kinds of sensitivity analysis are planned to be performed for the imputation of missing values for the primary safety endpoints. Sensitivity analysis will be performed if the main analysis results show significant effect.

Extreme cases analysis:

In case a subject withdraws from study prior to 6 months follow-up visit and without experiencing previously 'device/system related complication' or 'pressure sensor failure' respectively, the subject will be defined as

This document is confidential.

having experienced such an event for the 6 months analysis. Setting all missing events to 'Y' would be the only possible extreme cases value. After imputation, below analysis will be performed.

For endpoint 1:

```
proc freq data= xxx
    tables freedom (Y/N) / binomial(exact p=0.90 level = 1) ;
run;
define level = 1 'no event = no device/system related complication'
```

For endpoint 2:

```
proc freq data= xxx
    tables freedom (Y/N) / binomial(exact p=0.95 level = 1);
run;
define level = 1 'no event = no pressure sensor failure at 6 months'
```

Tipping point analysis:

If the null hypothesis is rejected for primary safety endpoint, a tipping point analysis will be conducted based on the binary response of freedom from event/with event at 6 months using similar manner as extreme cases analysis. For subjects withdraws from study prior to 6 months follow-up visit and without experiencing previously 'device/system related complication' or 'pressure sensor failure' respectively, setting all missing events to 'N', then gradually increasing the number of subjects with event at 6 months until null hypothesis is not rejected.

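### Six-minute walk: subjects unable to walk are left blank like those who refuse, so the observed-case change may lean towards improvement by an unknown amount

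*Protocol*

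**What the plan says.** **Recording.** Protocol 8.1.12 gives one rule for a walk that is not done: "If the Subject is unable or unwilling to perform the 6-minute walk test, the distance recorded should be left blank". No zero, worst score or reason code is given there. The rule applies at every scheduled walk, baseline included: "Subjects will complete a six (6) minute walk test at Screening, Month 6, 12 and 24", and then yearly from Year 3 to Year 5.

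**Missing data.** After dealing with the primary analyses, SAP 5.3 states: "For all other analysis, missing data will not be replaced".

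**Analysis.** SAP 7.1.17 states: "Total distance walked (meters) will be collected and analyzed by means of descriptive statistics including the absolute value and change from baseline by visit". The populations are mITT, PP and Cohort #1. There is no rule for death or inability, no rank-based method and no sensitivity analysis for the walk.

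**Role.** This is half of secondary efficacy endpoint 14 in SAP 3.3: "Functional status improvement, as measured by NYHA and 6-Minute Walk Test". No alpha is attached to it. SAP 2.4.2 says: "Any other calculated p-values and confidence intervals for secondary endpoints will be nominal, without adjustment for multiple comparisons".

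**General commitments.** Protocol 10.8 says "Sensitivity analyses to missing data will be conducted" and also undertakes to capture and summarise reasons for missing data. The only imputation-type analyses in the SAP are in 8.1.2: "Two kinds of sensitivity analysis are planned to be performed for the imputation of missing values for the primary safety endpoints".

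**The concern.** Being too ill to attempt the walk is the worst result the test can give. Protocol Appendix 14.3 allows usual walking aids, slowing, stopping and resting, and has staff check for contraindications first. A struggling walker therefore still gets a distance, and a health-related blank means the test could not be done at all. In the distance field that blank looks the same as a refusal, and it then leaves the analysis.

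The change from baseline is thus computed only in subjects with a distance at both Screening and the visit. A subject who walked at Screening and later became unable, or died, contributes nothing. In a single-arm trial no control group shows the same selection, so an observed-case gain cannot be separated from loss of the worst outcomes.

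The NYHA shift tables have a related weakness. Under SAP 12.2.4.2 the default percentage denominator is subjects with an observation, so the dead and the unassessed fall outside it.

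**Working it through.** The documents state no expected walk distance, SD, inability rate or effect size, so there is no plan figure to reproduce. The distances and inability rates below are assumptions; the deaths come from the planning table.

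**1. Selection effect when the true mean change is 0 m**

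Assumed: normal distances; baseline SD σb between 80 and 110 m; SD of change σd between 60 and 80 m; change unrelated to the baseline distance; and the share s with the shortest follow-up distance unable and left blank.

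The follow-up SD is √(σb² + σd²), and the covariance of change with follow-up distance is σd². Dropping the lowest share s at follow-up moves the mean change by

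shift = [φ(z_s)/(1 − s)] × σd² / √(σb² + σd²),

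where φ is the standard normal density and z_s its s-quantile. The first factor is 0.1031/0.95 = 0.1086 at s = 5% and 0.1755/0.90 = 0.195 at s = 10%.

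| σb, σd (m) | σd²/√(σb²+σd²) | s = 5% | s = 10% |
|---|---|---|---|
| 110, 60 | 3600/125.3 = 28.7 | +3.1 m | +5.6 m |
| 80, 80 | 6400/113.1 = 56.6 | +6.1 m | +11.0 m |

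A simulation with baseline means of 200 to 300 m agrees. Its observed-case change was +3.2 to +6.4 m at 5% and +5.7 to +11.2 m at 10%. Its true mean change was 0.3 to 1.6 m rather than exactly 0, because distances were cut off at 0 m.

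**2. When the shift is absent or reversed**

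- If inability is unrelated to walking ability, the observed-case change stays at the true value.
- Blanks at Screening push the other way. A separate simulation assumed baseline mean 250 m, SD 100 m, partial regression to the mean (slope 0.75), residual SD 70 m and true change about 0. It gave:

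| Unable at Screening | Unable at follow-up | Observed-case change |
|---|---|---|
| 0% | 10% | +5.7 m |
| 5% | 10% | +3.3 m |
| 5% | 5% | +0.3 m |
| 10% | 5% | −2.4 m |
| 10% | 0% | −4.9 m |

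The direction therefore depends on which visit loses more subjects.

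**3. Deaths, which can only fall after Screening**

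From the 6-month table in Protocol 10.3: CHAMPION 15/270 = 5.6%; MEMS-HF 16/234 = 6.8%; MEMS PAS 107/1200 = 8.9%. GUIDE-HF (NYHA III) gives only a 12-month death rate of 0.089. The protocol's own conversion gives 1 − √(1 − 0.089) = 4.6%. The planning studies thus span about 4.6% to 8.9%.

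**4. The summary chosen matters**

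Take an assumed observed-case change of +25 m and baseline of 250 m. Let s now be the share dead or unable.

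- *Mean, scoring them 0 m:* (1 − s) × 25 − s × 250 gives +11.3, −2.5 and −16.3 m at 5%, 10% and 15%. It is zero at s = 25/275 = 9.1%.
- *Median, giving them worst rank:* the median sits at the (0.5 − s)/(1 − s) quantile of the observed changes. With normal changes and SD 60 to 80 m it is about +20 to +21, +14 to +17 and +7 to +12 m at the same shares. It is zero at about 20% (SD 80 m) to 24% (SD 60 m).

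**The case against.** The strongest reply is that little depends on this. The walk has no hypothesis, alpha or success criterion. Deaths already count in the primary endpoint and in the mortality and days-alive-out-of-hospital analyses. A living subject too ill to walk can still be graded NYHA IV and can complete the KCCQ at home. SAP 12.2.4.2 adds a Missing category where data are absent, and SAP 6.1 tabulates subjects alive by visit. Because Appendix 14.3 lets subjects slow, stop and rest, few may be affected, some for non-cardiac reasons. All of this stands, and it limits the weight of the point. It does not repair the walk summary: a Missing row cannot tell deterioration from refusal, and the SAP applies Protocol 10.8's general commitments to nothing in endpoint 14.

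A reader might infer three stronger things that the documents do not support.

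- **The bias is certainly towards improvement.** The blank rule also applies at Screening, and Protocol 7.4 and 7.5 do not require subjects to be able to walk. Subjects unable at baseline are lost even if they later improve.
- **The sign of the change would flip at about 9% dead or unable.** That holds for a mean scoring those subjects 0 m, under assumed distances, and it gives all of them the average baseline although sicker subjects probably start lower. It mixes mortality into walk distance, which changes the estimand and does not measure bias. Under a worst-rank median the flip comes only at about 20% to 24%.
- **The reason for a missed walk is recorded nowhere.** Protocol 8.1.12 governs the distance field only. The eCRF is not among the documents, and Protocol 10.8 undertakes to capture reasons.

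**Conclusion.** The point holds in a limited form. The plan treats inability and refusal alike in the distance field, does not replace the blank, and summarises observed change only. The observed-case change leans towards improvement if inability at follow-up reflects worsening and exceeds inability at Screening; loss through death can act only after Screening. The size cannot be derived from the documents. Under the assumptions in step 1 it is about +3 to +6 m at 5% unable and +6 to +11 m at 10%. The primary and first secondary efficacy tests are untouched. The point is worth correcting because the endpoint is named as improvement, the trial has no control arm, and without a recorded reason no later analysis can separate deterioration from refusal.

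**What to change.** - **Protocol 8.1.12 and eCRF:** for every walk not performed, record the reason as unable for health reasons, unwilling, or logistic. For visits already held, recover the reason from source records where possible.
- **SAP 7.1.17, counts:** tabulate by visit, Screening included, the numbers who died, were unable for health reasons, were unwilling, or were otherwise not assessed. Show died and not-assessed counts in the NYHA shift tables.
- **SAP 7.1.17, sensitivity analysis:** pre-specify one analysis that gives death and health-related inability the worst rank (reporting the median change) or 0 m. Apply the same inability rule at Screening. Report it beside the observed-case summary, which can stay the main one; replacing it with a death-and-walk composite would be a debatable change of estimand.

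The cost is one eCRF field, some source review and a little more analysis. The downside for the sponsor is a possibly smaller reported improvement. The change is still useful, because walks continue to Year 5 and SAP 2.2 refreshes the full set of outputs at the follow-up analysis.
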